## **2. STUDY OBJECTIVES AND ENDPOINTS**

### **2.1. Objectives of The AXMUS-C Phase II Randomised Controlled Pilot study in colorectal cancer**

**Overall aims:** Axitinib has been used in the Phase II and III setting in many cancers, with an adequate safety profile. Its role in the treatment of colorectal cancer as monotherapy has yet to be defined.

- To evaluate the efficacy of Axitinib (a VEGF inhibitor) monotherapy in third-line metastatic colorectal cancer and improve clinical outcomes in chemotherapy- refractory metastatic CRC
- To test the potential for dynamic contrast-enhanced ultrasound as a potential novel imaging biomarker of early response against RECIST criteria

#### **Primary objective of trial**

- To demonstrate a progression-free survival to Axitinib monotherapy in refractory (to all known conventional treatments) metastatic colorectal cancer

#### **Secondary objectives of trial**

- To assess the correlation in patients with a confirmed vascular response (as evaluated by a greater than 20% reduction in CEPHI at 2 weeks).
  - This assessment will be done by separating out the RECIST-progressors (non-responders) who can also be detected by CEPHI at 2 weeks, and comparing this with RECIST responders (CR+PR+SD). The patients receiving Placebo will be included in this analysis.
  - To demonstrate the value of CEPHI as an early imaging selection biomarker of non-response (or response) in patients who have had at least 4 weeks of study treatment.
- To compare overall survival between the treatment and placebo arms
- To compare the overall RECIST response rate between the treatment and placebo arms
- To compare and correlate the 2 week CEPHI and 8 week RECIST response rates.
- To compare the median overall survival of patients receiving Axitinib who develop new diastolic hypertension (>90mmHg) with those that do not (in either/or the blinded placebo group or treatment group combined)
- To identify if CEPHI will function as a non-invasive correlative biomarker of Axitinib pharmacokinetics (PK) and help minimise toxicity and identify responders

CONFIDENTIAL

- Toxicity (CTC) i for the treatment and placebo arms

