### **Secondary objectives of trial**

- To assess the correlation in patients with a confirmed vascular response (as evaluated by a greater than 20% reduction in CEPHI at 2 weeks).
  - This assessment will be done by separating out the RECIST-progressors (non-responders) who can also be detected by CEPHI at 2 weeks, and comparing this with RECIST responders (CR+PR+SD). The patients receiving Placebo will be included in this analysis.
  - To demonstrate the value of CEPHI as an early imaging selection biomarker of non-response (or response) in patients who have had at least 4 weeks of study treatment.
- To compare overall survival between the treatment and placebo arms
- To compare the overall RECIST response rate between the treatment and placebo arms
- To compare and correlate the 2 week CEPHI and 8 week RECIST response rates.
- To compare the median overall survival of patients receiving Axitinib who develop new diastolic hypertension (>90mmHg) with those that do not (in either/or the blinded placebo group or treatment group combined)
- To identify if CEPHI will function as a non-invasive correlative biomarker of Axitinib pharmacokinetics (PK) and help minimise toxicity and identify responders
- Toxicity (CTC) i for the treatment and placebo arms

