### Secondary Endpoints

- To compare overall survival between the treatment and placebo arms
- To compare duration on study treatment between the treatment and placebo arms
- To compare the best overall RECIST response rate between the treatment and placebo arms
- To compare and correlate the 2-week CEHPI perfusion index and 8 week RECIST response rates in the ITT population
- To compare the median overall survival of patients receiving Axitinib who develop new diastolic hypertension ( $>90\text{mmHg}$ ) with those that do not (in either/or the blinded placebo group or treatment group combined)
- To identify if CEHPI will function as a correlative biomarker of Axitinib pharmacokinetics (PK) and help minimise toxicity and identify responders
- To compare toxicity (CTC) information for the treatment and placebo arms.
  - Type, incidence, severity, timing, seriousness of adverse events by Chemotherapy toxicity criteria (CTC) v4.03 grading.
- Axitinib PK analysis correlation with patients developing or not developing diastolic hypertension

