### 3. Study Design

A Phase II, double-blind, 2 arm pilot randomised placebo controlled trial. 50 patients will be sequentially randomised 2:1 to Axitinib or placebo.

Inclusion criteria: Chemorefractory third-line metastatic CRC with US-assessable liver or other abdominal metastases that can have a baseline DCEUS baseline measurement.

Treatment arm: Axitinib monotherapy started in all patients at 5mg bd, and increased fortnightly by a dose level (See Table 4) as tolerated to a maximum dose of 10mg bd.

Control arm: Placebo (blinded) randomised 2:1 to Axitinib : placebo

Follow up: Outpatient monitoring at 2 weeks and 4 weeks post first dose then 4 weekly thereafter with RECIST restaging every 8 weeks. CEHPI at baseline, 2 weeks and 8 weeks for assessment of differential blood supply (CEHPI) with an optional visit at 48-72 hours post first dose. VEGF-PK samples at Day 15 & Day 28 and at 8 weeks and RECIST progression. At 8 weeks, after tumour CT RECIST assessments, conventional responders (CR/PR/SD) continue monotherapy. In non-responders (PD), monotherapy can be continued if patient chooses to continue and if tolerated. CT response assessments continue at 8 weekly intervals in all patients, with parallel 8 weekly DCE-US. CEHPI at baseline, optionally at 47-72 hours, 2 weeks, 8 weeks and at progression of disease.

[figure not shown]

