## 9. Statistical Analysis

### 9.1 Size of treatment effect

This novel project is a Pilot Phase II double-blinded, placebo controlled randomised (2:1 Axitinib : Placebo) for 50 patients. This sample size would not normally allow for conventional or adequate powering of a study based on OS, PFS or RR. This is a pilot study of assessing efficacy of axitinib monotherapy in colorectal cancer. The primary end-point is PFS by conventional RECIST. If a difference of more than 6 weeks improvement in PFS is observed, then a funding application to Pfizer and UK NCRN will be made for an adequately powered phase III study.

As a secondary and exploratory analysis, the major interest is whether we can better select (or predict) the population that benefits from Axitinib within the next generation of study design. If our secondary hypothesis is correct, then in those patients who receive Axitinib, a significant proportion will have ultrasound detectable changes in reduction in blood flow. i.e. a significant pharmacodynamic effect on the tumour vasculature measured via the US biomarker index (CEPHI). In our preliminary work (Gauthier et al, 2011), a 20% change in CEPHI was significant and also allowed for measurement error. Thus, this study will therefore examine the survival difference between CEPHI responders (those whose CEPHI falls by  $\geq 20\%$ ) versus non-responders. A clinically meaningful difference in survival in these groups would be a difference of at least 6 weeks. If this end-point is achieved, it would be a positive signal to design an adequately powered phase III powered for OS. This would allow enrichment for patients who potentially benefit, but also allow discontinuation in patients at 2 weeks who will not benefit, saving unnecessary treatment and toxicities. This approach of personalised medicine using biomarkers (in this case CEPHI) is the direction of almost all cancer studies.

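### One secondary CEHPI objective, read literally, leaves out the RECIST progressors that CEHPI missed, which builds in an association and conflicts with sections 2.2 and 9.2

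*Combined protocol and SAP*

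**What the plan says.** The method stands under the secondary objectives, in the same words in the Trial Summary and section 2.1. A vascular response is defined "as evaluated by a greater than 20% reduction in CEPHI at 2 weeks". (The documents spell the index both CEHPI and CEPHI.) The assessment is to be done by "separating out the RECIST-progressors (non-responders) who can also be detected by CEPHI at 2 weeks, and comparing this with RECIST responders (CR+PR+SD". Both arms are pooled: "The patients receiving Placebo will be included in this analysis". The next sub-bullet seeks to show the value of CEHPI as an early selection marker "in patients who have had at least 4 weeks of study treatment".

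Other places put the CEHPI-RECIST question without this selection:

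- Section 2.1 has a separate bullet that compares and correlates the 2-week CEHPI and 8-week RECIST rates.
- Section 2.2, Secondary Endpoints: "To compare and correlate the 2-week CEHPI perfusion index and 8 week RECIST response rates in the ITT population".
- Section 9.2 plans a ROC curve of percentage change in CEHPI against RECIST response, with sensitivity, specificity, PPV, NPV and AUC for predicting progression.

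Section 9.2 neither repeats nor overrides the method given under the objectives, and no passage says which description governs.

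**The concern.** Taken as written, one group is defined by RECIST progression and a CEHPI non-response together. The other is defined by RECIST alone. So one side is selected on the variable being evaluated. A progressor with a CEHPI fall above 20% is an error of the marker, and that is the error this comparison cannot show.

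If the assessment were run this way, a marker with no information would look as if it separated progressors from responders. If the analyst instead followed section 2.2 or 9.2, the result could be quite different, and the protocol gives no basis for choosing between them before the data are seen.

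The 4-week condition is a second, separate problem. Section 9.1 hopes that CEHPI will allow patients who will not benefit to stop at 2 weeks. Whether a patient reaches 4 weeks of treatment is not known at that scan. Patients who stop between weeks 2 and 4, plausibly through rapid progression or toxicity, would be left out of the assessment of a 2-week tool.

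**Working it through.** **No figure to reproduce.** The documents give no sample size calculation, test, alpha or expected result for this comparison. The check asks how the literal rule behaves when CEHPI carries no information about RECIST.

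**Inputs from the documents**

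- Size: "50 patients will be sequentially randomised 2:1 to Axitinib or placebo" (section 3).
- Threshold: a fall above 20% at 2 weeks (section 2.1), so a progressor counts as detected if the fall is 20% or less.
- Arms pooled (section 2.1).

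**Assumptions**

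- Evaluable patients: 50, or 40 to allow for losses.
- Share with RECIST progression: 50% to 80%. The central value of 70% is suggested by the 29% best response of stable disease in the sunitinib study described in section 9.1.
- Share q with a CEHPI fall above 20%: 20% to 50%, central value 30%. Section 9.1 speaks only of a significant proportion.
- CEHPI independent of RECIST; two-sided Fisher exact test at 0.05.

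**Central case: 50 patients, 35 progressors, 15 responders, q = 0.30.** Expected counts:

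| | No fall above 20% | Fall above 20% |
|---|---|---|
| Progressors | 35 × 0.70 = 24.5 | 35 × 0.30 = 10.5 |
| Responders | 15 × 0.70 = 10.5 | 15 × 0.30 = 4.5 |

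With all four cells the expected odds ratio is (24.5 × 4.5)/(10.5 × 10.5) = 1, as it should be for noise. The literal rule removes the 10.5 missed progressors, so that cell becomes 0 and detection becomes 24.5/24.5 = 100%.

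**How easily the selected table becomes significant.** With 24 retained progressors, no falls among them, and 3 falls among 15 responders, the two-sided Fisher p is C(15,3)/C(39,3) = 455/9139 = 0.0498. With 23 retained it is 455/8436 = 0.0539. So with 24 or more retained, 3 falls among the responders are enough; with slightly fewer, 4 are needed.

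- P(24 or more retained), Binomial(35, 0.70): 0.652
- P(3 or more falls), Binomial(15, 0.30): 0.873
- P(4 or more falls), Binomial(15, 0.30): 0.703

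Rejection probability ≈ 0.652 × 0.873 + 0.348 × 0.703 = 0.569 + 0.245 = 0.814. Exact enumeration over all tables also gives 0.814. With all four cells kept it is 0.034.

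**Over the range of assumptions (exact enumeration)**

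| Evaluable | Literal rule | All four cells |
|---|---|---|
| 50 | 0.365 to 0.969 | 0.022 to 0.043 |
| 40 | 0.258 to 0.891 | 0.020 to 0.033 |

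The lowest value in each row comes from equal groups with q = 0.20, the highest from 70% progressors with q = 0.50. In every scenario the literal rule rejects far more often than 5%, and the full table stays below 5%.

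**The 4-week condition.** No arithmetic applies. Section 2.1 sets a minimum of 4 weeks of treatment for the biomarker objective, section 9.1 places the intended decision at 2 weeks, and section 2.2 sets the related CEHPI-RECIST endpoint in the ITT population.

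**The case against.** The strongest reply is that the objective is loosely worded and the plan already contains the right analysis. Section 2.1 names no statistic and no explicit exclusion. Separating out detected progressors could mean counting how many progressors CEHPI finds, that is, sensitivity, and setting that beside the responders. That reading agrees with section 9.2, whose sensitivity and NPV cannot be computed without the missed progressors. This stands in part: the literal reading is the natural one but not the only one. It does not remove the need for a change, because the sentence is phrased as the method of assessment and, taken at its word, gives a biased comparison.

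Three stronger readings are tempting and are not supported:

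- A reader might infer that all discordant patients are removed. Only progressors with a fall above 20% are; responders without such a fall are also discordant and stay in.
- A reader might infer that this is the only CEHPI-RECIST comparison. Sections 2.1 (separate bullet), 2.2 and 9.2 each describe an unselected one.
- A reader might infer that the phase III decision rests on it. Section 9.1 ties that step to survival by CEHPI status, with a difference of at least 6 weeks, and the CEHPI co-primary endpoint in section 2.2 is PFS by CEHPI status. Neither selects on RECIST.

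It is also fair that the trial is a pilot that disclaims power ("This sample size would not normally allow for conventional or adequate powering of a study based on OS, PFS or RR"), and that no Fisher test is planned here. The percentages therefore illustrate the bias; they are not error rates of a planned test.

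On the 4-week condition, the ITT endpoint in section 2.2 mirrors the separate correlation bullet, so a direct contradiction is arguable. The conditioning on later treatment is a defect either way.

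**Conclusion.** The point holds as a secondary-analysis correction. Under the literal wording, progressors missed by CEHPI drop out, detection among those retained is fixed at 100%, and the comparison is biased towards an association. With a useless marker, an illustrative Fisher test would reject in roughly 37% to 97% of trials with 50 evaluable patients (81% in the central case), against 2% to 4% for the full table. The size depends on assumed progression and CEHPI-fall rates and on a test that the plan does not name; the direction does not depend on the rates. The wording also disagrees with sections 2.2 and 9.2, and nothing says which governs.

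The restriction to at least 4 weeks of treatment is a separate and valid criticism, since it conditions on what happens after the scan that is meant to guide the decision. Neither defect touches the primary treatment comparison or the stated route to phase III.

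**What to change.** In the Trial Summary and section 2.1, replace the two sub-bullets with text such as: *All randomised patients with a baseline and a 2-week CEHPI will be cross-classified by CEHPI fall (above 20% versus 20% or less) and 8-week RECIST result (PD versus CR, PR or SD). All four cells will be reported, with sensitivity and specificity and their 95% confidence intervals, as part of the analysis in section 9.2.*

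Remove the 4-week treatment condition.

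Because patients with both scans are still not the ITT population, add to sections 2.2 and 9.2 the number of ITT patients without a 2-week CEHPI or an 8-week RECIST result and the rule for each, fixed before unblinding; for example, death or clinical progression before week 8 counted as PD. Align the cut-off at the same time: sections 2.1 and 2.2 define response as a fall above 20%, while section 9.1 includes a fall of exactly 20%.

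The cost is a few sentences and no new data. The apparent accuracy of CEHPI will be lower than under the selected comparison.

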The conventional PFS and OS for this cohort of chemo-refractory patients is 6-8 weeks and 4-6 months respectively. This is the first study with Axitinib in this setting. Our aim with 50 patients is to generate data for a sample size calculation for a randomised phase III. In the only comparative Phase 2 study (A6181003) with a similar compound, is of Sunitinib in chemorefractory metastatic colorectal cancer, 84 patients were enrolled and 82 were actually treated with Sunitinib. 10% discontinued due to adverse events. The ITT analyses for PFS was less than 2 months but OS still showed an encouraging overall survival of 10.2 months. Of greater interest, 1 patient with prior Bevacizumab therapy had a partial response; 24 patients (29%) had a best response of stable disease, 13 patients had SD  $\geq 22$  weeks. (This demonstrates the reason for doing our analysis as a sub-population has benefited significantly from Axitinib's parent compound and with CEPHI – we hope to predict this group). In our study, we would thus expect around 15-18 of the treated patients to have prolonged progression-free survival of this order of magnitude, and the placebo treated patients will act as a contemporaneous control. If the 2 week CEPHI index is highly predictive of survival in this group, then selection on this basis for a phase III trial will enrich the potentially benefitting population even further.

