## 9.2 Statistical analysis plan

The primary analysis will be on PFS by Kaplan-Meier of patients who manage to complete at least 2 weeks of Axitinib therapy (versus Placebo).

For the secondary analyses:-

A stratified log-rank test (1-sided,  $p=0.025$ ) will be used to compare PFS between CEHPI responders and non-responders. The median event time and 2-sided 95% CI for the median will be provided. The hazard ratio and its 95% CI will be also estimated.

The optimum CEHPI cut-point for determining response will be confirmed using the percentage change in CEHPI against RECIST response using a receiver operator characteristic curve. Test statistics including sensitivity, specificity, positive predictive value, negative predictive value, odds of disease progression and area under the curve will be calculated for 2 week CEHPI reduction in predicting disease progression.

A similar analysis will be performed with diastolic blood pressure.

Overall survival is defined as the time from date of randomisation to date of death due to any cause. For patients not expiring, their survival times will be censored at the last date they are known to be alive. Patients lacking data beyond the day of randomisation will have their survival times censored at the date of randomisation with duration of 1 day. Overall survival will be summarised using Kaplan-Meier methods and displayed graphically where appropriate. A stratified log-rank test (1-sided,  $p=0.025$ ) will be used to compare OS between CEHPI responders and non-responders. The median event time and 2-sided 95% CI for the median will be provided. The hazard ratio and its 95% CI will be also estimated.

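### The 4-week treatment condition on the CEHPI biomarker objective depends on events after the 2-week scan, and it is not reconciled with the ITT endpoint in 2.2 or the predictive analysis in 9.2

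*Combined protocol and SAP*

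**What the plan says.** The documents spell the index both CEHPI and CEPHI; CEHPI is used here.

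- **Trial Summary and 2.1, secondary objectives.** The first objective separates RECIST progressors from patients with CR, PR or SD by 2-week CEHPI, and adds: "The patients receiving Placebo will be included in this analysis". A sub-bullet under it seeks to show the value of CEHPI as an early selection biomarker, but only "in patients who have had at least 4 weeks of study treatment".
- **Same list, separate bullet with no restriction.** "To compare and correlate the 2 week CEPHI and 8 week RECIST response rates".
- **2.2, secondary endpoints.** "To compare and correlate the 2-week CEHPI perfusion index and 8 week RECIST response rates in the ITT population". No endpoint in 2.2 repeats the 4-week condition, and ITT is not defined anywhere.
- **9.2.** An ROC curve checks the CEHPI cut-point. Sensitivity, specificity, PPV, NPV and "area under the curve will be calculated for 2 week CEHPI reduction in predicting disease progression". No population is given. The primary PFS analysis in the same section uses a further rule, at least 2 weeks of therapy.
- **9.1.** The hoped-for use is to identify at week 2 the patients who will not benefit, so that they can stop then.

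**The concern.** A test read at week 2 should be judged in the patients who had it at week 2. The 4-week condition admits only those still on treatment two weeks later. Death, deterioration, toxicity or early progression in that interval can remove a patient, and some of these events are what the scan is meant to predict. Nobody applying the test at week 2 knows who will reach week 4, so predictive values from the 4-week subset do not describe that decision.

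Because 9.2 names no population, an analyst could use the 4-week set, some version of ITT, or the 2-week set, and could choose after seeing the data. The ROC check of the cut-point would inherit the choice. The trial is meant to inform enrichment of a phase III study. If early failures drop out of the set, a CEHPI fall looks more reassuring than it is, and the chance of progression without a fall looks lower than it is.

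**Working it through.** The documents give no expected predictive value, so there is no figure of theirs to reproduce. The size below is illustrative.

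**Inputs**
- 9.1: "The conventional PFS and OS for this cohort of chemo-refractory patients is 6-8 weeks and 4-6 months respectively". The PFS figure is read as a median of m = 6, 7 or 8 weeks for CEHPI non-responders.
- CEHPI responders are given a median of m + 6 = 12, 13 or 14 weeks. The 6-week gap is the difference that 9.1 calls clinically meaningful for survival; applying it to PFS is an assumption.
- N = 50 (section 3).
- f is the share of week 2 to 4 failures that also stop treatment before week 4. The documents do not give it, so it runs from 0 to 1.
- Failure times are exponential: S(t; m) = 2^(−t/m).

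**Step 1. Failures between the scan and week 4:** 50 × [S(2) − S(4)].
- m = 6: 50 × (0.794 − 0.630) = 8.2
- m = 7: 50 × (0.820 − 0.673) = 7.4
- m = 8: 50 × (0.841 − 0.707) = 6.7

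This puts all 50 patients at the plan's median. At medians of 12 to 14 weeks the count would be 4.9 to 4.3.

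**Step 2. Week-2 landmark set.** Among patients failure-free at week 2, PPV is the chance of failure by week 8 in CEHPI non-responders, 1 − S(6; m). NPV is the chance of no failure by week 8 in CEHPI responders, S(6; m + 6). At m = 7, PPV = 1 − 2^(−6/7) = 0.448 and NPV = 2^(−6/13) = 0.726.

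**Step 3. 4-week set, every early failure stopping (f = 1).** PPV = 1 − S(4; 7) = 0.327, a fall of 12.1 points. NPV = S(4; 13) = 0.808, a rise of 8.2 points.

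**Step 4. General f.** With q = 1 − S(2), the proportion failing by week 8 becomes [(1 − S(6)) − f·q] / (1 − f·q). For m = 7 and f = 0.5, q = 0.180 and PPV = (0.448 − 0.090) / (1 − 0.090) = 0.393.

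| f | PPV change, points (m = 6 / 7 / 8) | NPV change, points (responder median 12 / 13 / 14) |
|---|---|---|
| 0 | 0 / 0 / 0 | 0 / 0 / 0 |
| 0.25 | −2.7 / −2.6 / −2.5 | +2.0 / +1.9 / +1.8 |
| 0.5 | −5.8 / −5.4 / −5.1 | +4.1 / +3.9 / +3.7 |
| 0.75 | −9.2 / −8.6 / −8.1 | +6.3 / +6.0 / +5.7 |
| 1 | −13.0 / −12.1 / −11.3 | +8.7 / +8.2 / +7.7 |

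**Step 5. Deaths only.** If only deaths in weeks 2 to 4 are removed (5.2% to 7.7% at OS medians of 6 to 4 months), PPV falls by 2.7 to 4.9 points.

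**Step 6. Cases outside the table.** Leavers with no 8-week RECIST result who are dropped from both sets cause no difference. Leavers with stable disease push the other way. If a of n CEHPI non-responders progress and k stable leavers are removed, PPV goes from a/n up to a/(n − k). If b of n CEHPI responders do not progress and k of them leave, NPV goes from b/n down to (b − k)/(n − k).

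**The case against.** Four points can fairly be made against the concern.

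1. **Not one question with two populations.** A reader might infer a flat contradiction between 2.1 and 2.2. The documents do not support that. The ITT endpoint matches the separate, unrestricted bullet in 2.1, and that pair is consistent. The 4-week phrase belongs to a different sub-bullet with no endpoint of its own. This stands. What remains is that the sub-bullet concerns the same scan judged against RECIST outcome, under its own population, with no analysis that says which set applies.
2. **No analysis is shown to use the 4-week set.** True: 9.2 does not mention it. But 9.2 mentions no other population for the predictive values either, and the objective is the only text that attaches a treatment condition to this biomarker question.
3. **The week-2 decision in 9.1 rests on the survival difference between CEHPI groups, not on PPV or NPV.** This stands, and the matching co-primary endpoint in 2.2 has no 4-week condition. The timing argument is unaffected: a selection biomarker read at week 2 is used on everyone scanned at week 2.
4. **The condition is treatment duration, not freedom from progression.** The first scheduled RECIST scan is at week 8, and treatment may continue after progression (section 3, 6.4), so a patient progressing unseen at week 3 can stay in the set. Patients also leave for toxicity or by choice. This stands and limits the size. It does not remove the problem: 6.4 lists death, unacceptable toxicity and progression among the reasons for discontinuation, and 6.3 and 6.5.1 provide for continued imaging after stopping without progression, so some leavers will have a RECIST result that the 4-week rule discards.

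**Conclusion.** The concern holds as an unreconciled analysis population combined with a restriction that depends on events after the test. That selection flaw does not rest on any model.

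Its size does. A reader might infer that predictive values shift by about 12 points. That is an upper-end result for PPV alone: 11.3 to 13.0 points over medians of 6 to 8 weeks, with NPV moving 7.7 to 8.7. It requires every week 2 to 4 failure to stop treatment and to be counted as a non-responder. With a quarter to three quarters stopping, PPV falls by about 2.5 to 9 points and NPV rises by about 2 to 6. Depending on how early leavers are handled, the shift can be nil or reversed, so even the direction is likely rather than assured.

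The co-primary PFS comparison by CEHPI group is not affected. This is a secondary objective in a pilot that claims no power. It is worth correcting because the result is meant to guide phase III selection and the correction is cheap.

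**What to change.** - **Trial Summary and 2.1:** delete the 4-week condition from the selection-biomarker sub-bullet.
- **2.1, 2.2 and 9.2:** name one week-2 landmark population for the CEHPI-RECIST predictive analysis: *all randomised patients with a baseline and a 2-week CEHPI, whatever happens to treatment afterwards*. In 2.2 this replaces the reference to the ITT population, which cannot apply literally to patients who have no 2-week scan. Report how many randomised patients lack one.
- **9.2, early leavers:** for this analysis, count death or documented progression before the 8-week RECIST assessment as non-response. For patients who stop treatment without progression, use the continued imaging in 6.3 and 6.5.1. Report how many remain unclassified.
- **Sensitivity analysis:** show the 4-week subset only under that label.

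The cost is a few sentences in four places and no new data. The downside is that the apparent NPV may be less favourable.
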